5.3 Exclusion criteria

Patients eligible for this study must not meet **any** of the following criteria:

1. Patients that receive more than one iron chelator at the same time as current iron chelation treatment. (Patients who have received combination therapy in their medical history but are currently being treated with a single ICT agent are eligible.)
2. Patients continuing on deferoxamine or deferiprone in addition to study treatment. (Patients switching to or continuing on deferasirox are eligible).
3. Unresolved adverse events if the patient was previously treated with deferiprone or deferoxamine or deferasirox.

4. Significant proteinuria as indicated by a urinary protein/creatinine ratio $> 0.5 \text{ mg/mg}$ in a non-first void sample urine measured at screening visit 1.
5. Serum creatinine $>$ age adjusted ULN measured at any screening visit
6. Creatinine clearance below 90 mL/minute measured at any screening visit. Creatinine clearance using the Schwartz formula will be estimated from serum creatinine measured at each respective visit.
7. ALT and/or AST $> 2.5 \times \text{ULN}$ measured at screening visit 1.
8. Total bilirubin (TBIL) $> 1.5 \times \text{ULN}$ measured at screening visit 1.
9. Patients with significant impaired GI function or GI disease that may significantly alter the absorption of oral deferasirox FCT (e.g. ulcerative diseases, uncontrolled nausea, vomiting, diarrhea, malabsorption syndrome, or small bowel resection).
10. History of and/or laboratory evidence of active Hepatitis B or Hepatitis C (HBsAg in the absence of HBsAb OR HCV Ab positive with HCV RNA positive).
11. Liver disease with severity of Child-Pugh Class B or C.
12. History of hypersensitivity to any of the study drug or excipients.
13. Patients participating in another clinical trial or receiving an investigational drug.
14. Patients with a known history of HIV seropositivity.
15. Patients unwilling or unable to comply with the protocol.
16. History of malignancy of any organ system, treated or untreated, within the past 5 years whether or not there is evidence of local recurrence or metastases, with the exception of localized basal cell carcinoma of the skin.
17. Significant medical condition interfering with the ability to partake in this study (e.g. uncontrolled hypertension, unstable cardiac disease not controlled by standard medical therapy, systemic disease: cardiovascular, renal, hepatic, etc.).

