6.3 Dose modifications

6.3.1 Dose modification and dose delay

For patients who do not tolerate the protocol-specified dosing schedule, dose interruptions and/or reductions are either recommended or mandated in order to allow patients to continue the study treatment.

These dose modifications are summarized in [Table 6-4](#). Deviations to mandatory dose interruptions and/or reductions are not allowed. Permanent treatment discontinuation is mandatory for specific events indicated as such in [Table 6-4](#) or listed in [Section 7.1.5](#).

These dose changes must be recorded on the Dosage Administration Record CRF.

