Single serum creatinine increase $\geq 33\%$ above baseline value and $> \text{ULN}$	
Deferasirox dose reduction by 7 mg/kg/day for the FCT is necessary.
 
If after dose reduction, resolution of serum creatinine occurs (<33%) and within normal limits, dose can be re-escalated to 100% of the last dose.
 
If increase in serum creatinine recurs again within 2 months according to guidelines above, therapy needs to be reduced to 50% of the last dose
 
After 2 months, if the serum creatinine increase does not recur, study medication may be re-escalated to 100% of the last dose depending on the clinical judgement of the investigator.
 
If after an initial dose reduction, a progressive increase in serum creatinine beyond the ULN is observed, or SCr increases re-occur repeatedly at adequate dose, a treatment interruption is recommended.
 
After a treatment interruption, if serum creatinine falls below the age-appropriate ULN on two consecutive visits, it is recommended to resume therapy at 50% of the last dose, and after 1 month, if the serum creatinine increase does not recur, study medication can be returned to 100% of the last dose (including body weight adjustment if required) depending on the clinical judgement of the investigator.

Patients who met the eligibility criteria and who experience a renal function decrease $< \text{LLN}$ ($\text{CrCl} < 90 \text{ml/min}$) at 2 consecutive visits	
If decrease cannot be attributed to other causes, DFX must be dose reduced by 7mg/kg/day.
 
If after dose reduction the renal function increases $>$

Recommended dose modifications for deferasirox

LLN (CrCl >90ml/min), dose may be re-escalated to the last daily dose prior dose reduction depending on the clinical judgement of the investigator.
If after dose reduction the renal function remains <LLN (CrCl <90ml/min), treatment must be interrupted.
Treatment may be reinitiated depending on the clinical judgement of the investigator.
If creatinine clearance falls below 60ml/min study treatment must be discontinued.

Investigations (Hepatic)**Isolated direct (conjugated) Bilirubin elevation**

> ULN – 1.5 x ULN

Maintain dose level

> 1.5 - 3.0 x ULN

Omit dose with weekly monitoring of LFTs, or more frequently if clinically indicated, until resolved to \leq 1.5 x ULN.

If resolved in \leq 14 days, then maintain dose level

If resolved in > 14 days, then dose reduction of 3.5 or 7 mg/kg/day for deferasirox FCT.

> 3.0 - 10.0 x ULN

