Omit dose with weekly monitoring of LFTs, or more frequently if clinically indicated, until resolved to \leq 1.5 x ULN.

If resolved in \leq 14 days, then dose reduction of 3.5 or 7 mg/kg/day for deferasirox FCT

If resolved in > 14 days, then discontinue patient from study drug treatment. The patient needs to be monitored weekly (including LFTs), or more frequently if clinically indicated until TBIL have resolved to baseline or stabilization. Please refer to section 6.3.3 for additional details on follow-up.

> 10.0 x ULN*

Discontinue patient from study drug treatment
The patient needs to be monitored weekly (including LFTs), or more frequently if clinically indicated, until TBIL have resolved to baseline or stabilization. Please refer to section 6.3.3 for additional details on follow-up.

AST or ALT elevation

> ULN - 3.0 x ULN

Maintain dose level

> 3.0 - 5.0 x ULN

(For patients with baseline value \leq 3.0 x ULN)

(For patients with baseline value > 3.0 -5.0 x ULN)

> 5.0 - 10.0 x ULN

(For patients with baseline value > 3.0 -5.0 x ULN)

> 5.0 - 10.0 x ULN

(For patients with baseline value \leq 3.0 x ULN)

> 10.0 - 20.0 x ULN

Maintain dose level.

Repeat LFTs as soon as possible, preferably within 48-72 hours from awareness of the abnormal results; if abnormal lab values are confirmed upon the repeat test, then monitor LFTs weekly, or more frequently if clinically indicated, until resolved to $\leq 3.0 \times$ ULN. Please refer to section 6.3.3 for additional details on follow-up.

Maintain dose level.

Omit dose.

Repeat LFTs as soon as possible, preferably within 48- 72 hours from awareness of the abnormal results; monitor LFTs weekly, or more frequently if clinically indicated, until resolved to $\leq 3.0 \times$ ULN
If resolved in ≤ 14 days, maintain dose level
If resolved in > 14 days, then dose reduction of 3.5 or 7 mg/kg/day for deferasirox FCT.

Omit dose.

Repeat LFTs as soon as possible, preferably within 48-

Confidential

6 Protocol No.

Page 40

Recommended dose modifications for deferasirox**> 20.0 x ULN**

(For patients with baseline value > 3.0 -5.0 x ULN)

72 hours from awareness of the abnormal results; monitor LFTs weekly, or more frequently if clinically indicated, until resolved to \leq baseline. Then dose reduction of 3.5 or 7 mg/kg/day for deferasirox FCT.

Discontinue patient from study drug treatment

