Repeat LFTs as soon as possible, preferably within 48-72 hours from awareness of the abnormal results; monitor LFTs weekly, or more frequently if clinically indicated, until resolved to baseline or stabilization. Please refer to section 6.3.3 for additional details on follow-up of toxicities.

Combined elevations of AST or ALT and total bilirubin

For patients with normal baseline ALT or AST or total bilirubin value:

AST or ALT >3.0xULN combined with total bilirubin >2.0 x ULN without evidence of cholestasis

OR

[AST or ALT>2x baseline AND > 3.0 xULN] OR [AST or ALT > 8.0 xULN], whichever is lower, combined with [total bilirubin >2x baseline AND >2.0 xULN]

Interrupt study treatment.

Permanently discontinue patient from study drug treatment if no other plausible explanation can be found for the combined increase.

Repeat as soon as possible, preferably within 48 hours from awareness of the abnormal results, then with weekly monitoring of LFTs, or more frequently if clinically indicated, until AST, ALT, or bilirubin have resolved to baseline or stabilization.

Please refer to section 6.3.3 for additional details on follow-up of toxicities.

Hepatic impairment

Moderate hepatic impairment (Child- Pugh Class B

The study medication will be interrupted and patient monitored. If liver disease prognosis improves, deferasirox can be reintroduced at 7 mg/kg/day for FCT or 50% of previous dose, whichever is less. While monitoring continues, dose may be increased by 3.5 mg/kg/day for FCT every 2 weeks, to a maximum of 50% of patient's previous dose if the investigator determines that dose increase is in the best interest of the patient. Study medication must be used with caution in such patients.

In patients who develop severe hepatic impairment (Child-Pugh Class C) during the study

Study medication must be discontinued.

Other recommended dose modifications**Changes in Serum Ferritin**

500 – 1000 ng/mL

The dose of deferasirox FCT should be adjusted as necessary every 3 months based on the trends in serum ferritin and investigator's judgement.

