7.2.2.5 Laboratory evaluations

Clinical laboratory parameters will be assessed as detailed in [Table 7-2](#).

Table 7-2 Local Clinical laboratory parameters collection plan

Test Category	Test Name
Hematology	Hematocrit, Hemoglobin, MCH, MCHC, MCV, Platelets, Red blood cells, White blood cells, Differential (Basophils, Eosinophils, Lymphocytes, Monocytes, Neutrophils)
Chemistry	Alkaline phosphatase, ALT, AST, Creatinine, Creatinine clearance, Direct Bilirubin, Total Bilirubin, Blood Urea Nitrogen (BUN) or Urea, Uric acid, Total protein, Bicarbonate, Albumin, Chloride, Glucose, Inorganic phosphate, Potassium, Sodium, Calcium and Magnesium.
Urinalysis	Microscopic Panel (Red Blood Cells, White Blood Cells, Casts, Bacterial casts Macroscopic Panel (Dipstick): Color, Bilirubin, WBCs, Blood, Glucose, Ketones, Nitrite, pH, Protein, Specific Gravity, Urobilinogen Urinalysis: Urine protein/creatinine ratio
Hepatitis markers	HBsAg, Anti-HCV, Anti-HBs, HCV RNA-PCR quantitative (screening visit 1)

Analysis of all laboratory specimens including urinary dipstick analysis will be performed by a local laboratory.

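### Table 6-4's bilirubin block is triggered by direct bilirubin, but weekly monitoring after discontinuation ends on total bilirubin, and the threshold that selects the 14-day branch names no analyte

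*Protocol*

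**What the plan says.** Protocol Table 6-4, Investigations (Hepatic), opens its bilirubin block with the heading "Isolated direct (conjugated) Bilirubin elevation". Four tiers follow, in multiples of the ULN.

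- **>ULN-1.5:** the dose is maintained.
- **>1.5-3.0:** "Omit dose with weekly monitoring of LFTs, or more frequently if clinically indicated, until resolved to" ≤1.5 × ULN. If this takes 14 days or less, the dose level is kept. If it takes longer, the dose is reduced.
- **>3.0-10.0:** the same omission and the same ≤1.5 × ULN threshold. Resolution within 14 days leads to a dose reduction, and later resolution to discontinuation. After discontinuation the child is monitored weekly, or "more frequently if clinically indicated until TBIL have resolved to baseline or stabilization".
- **>10.0:** discontinuation, with weekly monitoring until "TBIL have resolved to baseline or stabilization".

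TBIL is defined as total bilirubin in the list of abbreviations. The protocol treats the two analytes as separate. The next block of Table 6-4 is headed "Combined elevations of AST or ALT and total bilirubin". The chemistry panel in Table 7-2 lists "Direct Bilirubin, Total Bilirubin" side by side. SAP Table 2-1 gives each its own notable-value row.

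**The concern.** A stopping rule for monitoring should refer to the measurement that started it. Here the rule starts on direct bilirubin and, after discontinuation, stops on total. The two have different reference limits and need not fall together. A site that follows the row exactly could end weekly liver monitoring in a child aged 2 to <6 years while the value that forced discontinuation is still high.

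The second problem is the resolution threshold. The rows give ≤1.5 × ULN without repeating the analyte. The heading suggests direct, but the >3.0-10.0 cell moves on to TBIL. Sites reading this differently could take different treatment actions on the same laboratory results. Those actions feed reported outputs: interruptions and reductions (SAP 2.6.4), and adverse events leading to discontinuation or dose adjustment (SAP 2.11.1). Protocol 6.3.1 also states "Deviations to mandatory dose interruptions and/or reductions are not allowed", so rows written as instructions need one reading.

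**Working it through.** The plan gives no figure to reproduce. The check sets the wording side by side and then applies it to discordant values.

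**Step 1. Which analyte governs each step of the block**

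| Step | Tiers | Analyte |
|---|---|---|
| Trigger for omission or discontinuation | all | direct (heading) |
| Resolution to ≤1.5 × ULN, which selects the 14-day branch | >1.5-3.0 and >3.0-10.0 | not named in the row |
| End of weekly monitoring after discontinuation | >3.0-10.0 (beyond 14 days) and >10.0 | TBIL |

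TBIL does not appear in the >1.5-3.0 tier, and no trigger names it.

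**Step 2. End of monitoring**

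The documents give no reference limits, so these are assumptions: total ULN 1.0 mg/dL, and direct ULN from 0.2 to 0.4 mg/dL. Take a child already discontinued for direct bilirubin. At a later weekly check total is 1.4 mg/dL, equal to the child's baseline, and direct is 0.7 mg/dL.

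- Total: 1.4 / 1.0 = 1.4 × ULN. This is an eligible baseline, because Protocol 5.3 excludes only >1.5 × ULN. The TBIL end point is met.
- Direct, ULN 0.2: 0.7 / 0.2 = 3.5 × ULN.
- Direct, ULN 0.3: 0.7 / 0.3 = 2.3 × ULN.
- Direct, ULN 0.4: 0.7 / 0.4 = 1.75 × ULN.

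Across this range direct bilirubin is still above the block's own 1.5 × ULN threshold, yet weekly monitoring may stop. How far above depends on the assumed limit: only at 0.2 does the value still lie in the >3.0-10.0 band.

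**Step 3. The 14-day branch**

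Take a hypothetical child in the >3.0-10.0 tier whose direct bilirubin falls from 4 to 1.4 × ULN by day 14, while total is 1.6 × ULN.

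- Threshold read as direct: 1.4 ≤ 1.5, so resolved within 14 days. The dose-reduction branch applies.
- Threshold read as total: 1.6 > 1.5, so not resolved. Omission continues past day 14, and the discontinuation branch applies.

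The same results lead to two different actions.

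**Step 4. What other sections supply**

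- Protocol 6.3.3, cross-referenced from the discontinuation rows, requires at least 30 days of follow-up and follow-up of unresolved toxicities to Grade 1 or lower, baseline, stabilization or loss to follow-up.
- Protocol 7.1.7 requires unresolved adverse events to be followed until resolved or the child is lost to follow-up.
- Protocol 8.1.2.1 requires laboratory abnormalities that qualify as adverse events to be followed until normal or explained. Under 8.1.1, one that requires a change of study medication qualifies.

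These keep the child under observation. None sets a weekly interval or names the bilirubin fraction, so none resolves steps 2 and 3.

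**The case against.** The strongest reply is that the heading governs the whole block, so every unnamed threshold beneath it means direct bilirubin. TBIL then appears only after drug has been permanently stopped, where it cannot alter dosing, and the sections in step 4 keep follow-up going. Much of this stands. The heading is the natural source for the unnamed analyte, and the loss at the end of monitoring is mainly the weekly frequency. It does not remove the trigger/stop mismatch, which is in the text twice. Nor does it make the 14-day threshold unambiguous in a cell that also names TBIL.

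A reader might infer three stronger things, which the documents do not support.

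- *That which children have drug omitted depends on the analyte a site chooses.* It does not. With the assumed limits of 1.0 and 0.2 mg/dL, a child with total 1.8 and direct 0.2 mg/dL is at 1.8 × ULN on total and 1.0 × ULN on direct. Under the heading no tier applies, and another answer requires ignoring the heading.
- *That the total-bilirubin exclusion in Protocol 5.3 conflicts with a direct-bilirubin dose rule.* Entry screening and dose modification serve different purposes and may use different analytes.
- *That a child with raised direct bilirubin leaves follow-up altogether.* Sections 6.3.3, 7.1.7 and 8.1.2.1 say otherwise.

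The >10.0 tier carries an asterisk with no matching footnote in the available text. If the footnote exists, it should be checked, as it could bear on that row.

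**Conclusion.** The point holds as a contradiction of limited scope within a safety rule. The end of weekly monitoring does not track the analyte that caused discontinuation in the >3.0-10.0 (unresolved beyond 14 days) and >10.0 × ULN tiers. The ≤1.5 × ULN threshold should name its analyte because it selects the 14-day branch.

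The size cannot be put as a rate. How often direct and total bilirubin would diverge in these children is not derivable from the documents, and the worked values are hypothetical with assumed reference limits. The conclusion about wording does not depend on them. Sample size and the primary gastrointestinal analysis are unaffected. Any effect on reported results would come through interruption, reduction and discontinuation counts by way of the 14-day branch.

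**What to change.** The sponsor should reconcile the heading of the bilirubin block in Table 6-4 with the TBIL wording in its discontinuation rows. Each row should state which analyte, or both, governs (a) resolution to ≤1.5 × ULN and (b) the end of weekly monitoring. Any footnote to the top tier should be checked at the same time. No view is taken here on which analyte or threshold is clinically right.

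The cost is table wording in an amendment and notice to sites. No new tests are needed, since both analytes are already measured at the same chemistry visits (Protocol 7.2.2.5.2).

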6.3.3.1 Follow up on potential drug-induced liver injury (DILI) cases

Patients with transaminase increase combined with TBIL increase may be indicative of potential DILI, and should be considered as clinically important events.

The threshold for potential DILI may depend on the patient's baseline AST/ALT and TBIL value; patients meeting any of the following criteria will require further follow-up as outlined below:

- For patients with normal ALT and AST and TBIL value at baseline: AST or ALT $> 3.0 \times$ ULN combined with TBIL $> 2.0 \times$ ULN
- For patients with elevated AST or ALT or TBIL value at baseline: [AST or ALT $> 2 \times$ baseline AND $> 3.0 \times$ ULN] OR [AST or ALT $> 8.0 \times$ ULN], combined with [TBIL $> 2 \times$ baseline AND $> 2.0 \times$ ULN]

Medical review needs to ensure that liver test elevations are not caused by cholestasis, defined as ALP elevation $> 2.0 \times$ ULN with R value < 2 in patients without bone metastasis, or elevation of ALP liver fraction in patients with bone metastasis.

Note: (The R value is calculated by dividing the ALT by the ALP, using multiples of the ULN for both values. It denotes whether the relative pattern of ALT and/or ALP elevation is due to cholestatic (R ≤ 2), hepatocellular (R ≥ 5), or mixed (R > 2 and < 5) liver injury).

In the absence of cholestasis, these patients should be immediately discontinued from study drug treatment, and repeat LFT testing as soon as possible, preferably within 48 hours from the awareness of the abnormal results. The evaluation should include laboratory tests, detailed history, physical assessment and the possibility of liver metastasis or new liver lesions, obstructions/compressions, etc. Data and test results must be entered in the hepatotoxicity follow up test procedures eCRFs available in the clinical database.

1. Laboratory tests should include ALT, AST, albumin, creatine kinase, total bilirubin, direct and indirect bilirubin, GGT, prothrombin time (PT)/INR and alkaline phosphatase.
2. A detailed history, including relevant information, such as review of ethanol, concomitant medications, herbal remedies, supplement consumption, history of any pre-existing liver conditions or risk factors, should be collected.
3. Further testing for acute hepatitis A, B, C or E infection and liver imaging (e.g. biliary tract) may be warranted.
4. Obtain PK sample, as close as possible to last dose of study drug, if PK analysis is performed in the study.

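### Table 6-4 and section 6.3.3.1 give the same combined liver trigger to different baseline populations, so an eligible child with one raised baseline value can, within bounded ranges, meet one and not the other.

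*Protocol*

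**What the plan says.** Two places in the Protocol describe a combined rise in transaminases and bilirubin.

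- **Table 6-4, combined elevations of AST or ALT and total bilirubin.** The row opens with "For patients with normal baseline ALT or AST or total bilirubin value". Its fixed trigger is "AST or ALT >3.0xULN combined with total bilirubin >2.0 x ULN without evidence of cholestasis". A second criterion, built on multiples of baseline, follows after an OR. The action is to interrupt, and then: "Permanently discontinue patient from study drug treatment if no other plausible explanation can be found for the combined increase". The row refers to section 6.3.3 for follow-up.
- **Section 6.3.3.1, potential drug-induced liver injury.** The fixed trigger is given "For patients with normal ALT and AST and TBIL value at baseline". The baseline-multiple criterion is given "For patients with elevated AST or ALT or TBIL value at baseline". The action is: "In the absence of cholestasis, these patients should be immediately discontinued from study drug treatment". Cases confirmed on repeat testing with no alternative cause are to be reported as SAEs.

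Two other sections matter. Section 5.3 excludes ALT or AST above 2.5 x ULN and total bilirubin above 1.5 x ULN, each measured at screening visit 1. Section 6.3.1 allows no deviation from mandatory interruptions or reductions and makes permanent discontinuation mandatory where Table 6-4 says so.

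**The concern.** Read as written, the table's condition is satisfied if any one of the three baseline values is normal. The condition in 6.3.3.1 is satisfied only if all three are. A child with exactly one raised value at baseline is therefore in the fixed-trigger group of the table and in the baseline-multiple group of 6.3.3.1. Eligibility lets such children in.

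The table's rule is binding, and it sends the reader to the section that contains the other version. Two sites could handle identical laboratory values differently, one interrupting under the table and the other applying the 6.3.3.1 condition and finding no trigger. AEs leading to discontinuation are part of a secondary safety endpoint (Protocol Table 3-1 and 10.5), and the SAP (2.11.1) also tabulates AEs requiring dose adjustment or interruption.

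**Working it through.** The plan states no figure on this point. The check writes both passages as logical rules and finds where they part.

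**Inputs** (multiples of ULN; normal means at most 1.0; no cholestasis)

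- Fixed trigger: ALT or AST > 3 and TBIL > 2 (both passages).
- Baseline-multiple trigger: a transaminase that is > 2 x its own baseline and > 3, or is > 8; together with TBIL > 2 x baseline and > 2 (6.3.3.1).
- Eligible range: ALT/AST up to 2.5, TBIL up to 1.5 (5.3).

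**Band (a): one transaminase raised at baseline, value b; the other two normal.** TBIL baseline is at most 1.0, so 2 x baseline is at most 2 and the bilirubin parts agree. The transaminase limit in 6.3.3.1 is the larger of 3 and 2b.

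- If b is at most 1.5, then 2b is at most 3 and the passages agree.
- If b is above 1.5 and up to 2.5, they disagree for on-study values above 3 and up to 2b, at most 2 x 2.5 = 5, with TBIL > 2.
- The other transaminase must not qualify by itself. Its baseline is normal, so any value above 3 would satisfy 6.3.3.1.

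**Band (b): TBIL raised at baseline, value t; both transaminases normal.** Any transaminase above 3 meets that part of both rules. The bilirubin limit in 6.3.3.1 is 2t, so the passages disagree for on-study TBIL above 2 and up to 2t, at most 2 x 1.5 = 3, with ALT or AST > 3.

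A grid in steps of 0.1 x ULN (AST held at 1.0) gave the same bands:

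| Baseline elevation | Fixed trigger met, 6.3.3.1 not met |
|---|---|
| ALT 1.1, 1.3 or 1.5 | none |
| ALT 1.6 | ALT 3.1 to 3.2 |
| ALT 2.0 | ALT 3.1 to 4.0 |
| ALT 2.5 | ALT 3.1 to 5.0 |
| TBIL 1.1 | TBIL 2.1 to 2.2 |
| TBIL 1.5 | TBIL 2.1 to 3.0 |

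**Examples**

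1. Baseline ALT 2.0, AST 0.9, TBIL 0.8; on study ALT 3.5, AST 2.0, TBIL 2.2. Fixed trigger: 3.5 > 3 and 2.2 > 2, met. Section 6.3.3.1: 3.5 is below 2 x 2.0 = 4.0 and below 8, not met.
2. Baseline ALT and AST 0.9, TBIL 1.4; on study ALT 3.5, AST 2.0, TBIL 2.5. Fixed trigger met. Section 6.3.3.1: 2.5 is below 2 x 1.4 = 2.8, not met.
3. Contrast: the baseline of example 1, on study ALT 4.1, AST 2.0, TBIL 2.2. Now 4.1 > 4.0, and both passages are met.

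**All three values raised at baseline.** Read literally, this child falls under the baseline-multiple criterion of 6.3.3.1 but outside the table's printed heading.

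**The case against.** The strongest reply is that a site can obey both passages. Section 6.3.1 assigns dose changes to Table 6-4, and 6.3.3.1 defines cases for further follow-up. Nothing in 6.3.3.1 tells a site to continue the drug in a child who falls short of its criteria. A broad interruption trigger with a narrower case definition would be coherent. This stands as a possible intention, but the Protocol does not state it. The thresholds are the same in both places, the populations differ by one conjunction, and 6.3.3.1 also orders discontinuation, so it is not only a follow-up definition.

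A reader might infer four stronger things, which the documents do not support:

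- **That SAE counts depend on which passage a site uses.** Section 6.3.3.1 ties the SAE to its own laboratory criteria, and this row of Table 6-4 contains no SAE instruction.
- **That every child with one raised baseline value is affected.** Outside the bands the passages agree.
- **That the table stops treatment outright.** It interrupts first and discontinues permanently only if no other plausible explanation is found.
- **That any on-study value in a band changes the dosing.** With ALT above 5 x ULN, the separate transaminase row of Table 6-4 appears to omit the dose anyway. At 3.5 x ULN, as in the examples, that row appears to maintain it, so the combined trigger decides. The cells are displaced in the extracted text, so this reading is tentative.

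A heading for the table's second criterion may likewise have been lost in extraction. If so, the remark on three raised values may fall away. The main conflict does not: the printed condition already puts a child with one elevation under the fixed trigger.

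Rarity also counts against a large effect. The Protocol (1.2.1.2) reports ALT above 5 x ULN in 4.3% of children in a 5-year study, and SAP 2.11.5.4 calls hepatic cases rare for this compound. The SAP's potential Hy's Law table (2.11.4) uses fixed thresholds whatever the baseline, so it depends on neither passage.

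**Conclusion.** The point holds as an inconsistency of wording in a binding liver-safety rule. For eligible children with exactly one baseline elevation, the passages disagree in two bands:

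- a transaminase above 1.5 and up to 2.5 x ULN at baseline, then above 3 x ULN and up to twice baseline;
- bilirubin above 1.0 and up to 1.5 x ULN at baseline, then above 2 x ULN and up to twice baseline.

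Each band also needs the companion conditions shown in the working.

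The likely number of children is small, and the documents give no basis for estimating it. With 40 patients, one child is 1/40 = 2.5 percentage points of any discontinuation rate; that is the weight of a single case, not a forecast. The effect is on consistent interruption and discontinuation, and so on AEs leading to discontinuation. The primary gastrointestinal endpoint, SAE reporting and the sample size are untouched.

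The bands assume no cholestasis and take the screening visit 1 limits as baseline limits. The SAP (2.1.2.6) defines baseline as the last value on or before first dose, and chemistry is repeated at Week 1, so actual baselines may lie outside those limits and the bands would move with them.

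**What to change.** Reconcile the combined-elevation row of Table 6-4 with section 6.3.3.1 in one of two ways:

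- state the same baseline population for each criterion in both places, with its own heading in the table for the fixed and for the baseline-multiple criterion; or
- state explicitly that the table's interruption trigger is meant to be broader than the 6.3.3.1 case definition.

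Either way, say how a child with all three values raised at baseline is covered. The sponsor's clinical team must choose the trigger; none is proposed here. The cost is Protocol wording, by amendment or clarification letter. No new data, assessments or analyses are needed.
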